Title: Dementia Caregiver Career Study

NCT04603482

Date: February 1, 2023

HRP- 503SBER	TEMPLATE: SBER Protocol		
Approved:	01/2019	Prior Version:	05/2018

[USE THIS SOCIAL, BEHAVIORAL, AND EDUCATIONAL PROTOCOL TEMPLATE IF YOUR PROJECT INCLUDES SURVEY, INTERVIEWS, FOCUS GROUPS OR EDUCATIONAL RESEARCH ACTIVITIES WITH NO BIOMEDICAL/CLINICAL COMPONENTS]

INSTRUCTIONS:

- Use this template to prepare a document with the information from the following sections.
- Depending on the nature of what you are doing, some sections may not be applicable to your research. If so, please mark as N/A. You may delete contents of sections, but will not be able to delete the headings of the sections.
- When you write a protocol, keep an electronic copy. You will need to modify this copy when making changes.
- Consider using a different color font for your answers.

PROTOCOL TITLE:

Self-Management Intervention: Considering Needs & Preferences of Dementia Caregivers

(aka “Caregiver Career Study”)

PRINCIPAL INVESTIGATOR

[name]
 Nursing Science
 [contact]
[contact]

UH FACULTY ADVISOR:

If the principal investigator's primary role at UH is resident, fellow or student, identify a faculty advisor.

N/A

OTHER DEPARTMENTS INVOLVED IN THIS STUDY (IF APPLICABLE):

VERSION NUMBER:

Include the version number of this protocol if assigned by an outside entity.

DATE:

V1	12/19/19
V2	Updated 1.3.20
V3	Updated 10.7.2020, 11.23.20
V4	Updated 2.18.21, 5.14.21
V5	Updated 8.29.22
V6	Updated 2.1.23

Indicate the origin of this protocol (who conceived of and leads the development of the protocol regardless of funding):

- Investigator initiated (*Investigator(s) developed protocol, regardless of funding*)
- Industry (*Pharmaceutical, Device, etc.*) (*Industry developed protocol*)
- Federal (*NIH, DOD, etc.*)
- Cooperative Group (*SWOG, GOG, etc.*)
- Other - *Please specify:*

Funding

Objectives

Our **primary aim** is to examine the effects of a health self-management intervention (Biofeedback or Resourcefulness Training) delivered by need or preference in family carers of persons with dementia on caregiving responses (**1a**) and health outcomes (**1b**) over time. We hypothesize that family carers who receive either Biofeedback Training (BF) or Resourcefulness Training (RT) based on need or preference will have better health outcomes than carers in the attention control condition, regardless of caregiving phase.

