The data collection for caregivers sampled involves three structured face-to-face sessions with data collectors, each lasting typically 60-90 minutes. Data will be collected at baseline (T1), at 4-6 months (T2) after the 4-week intervention, and at 12-4-6 months later (T3). The data collection includes measures of carer health conditions, carer life events, health rating of care recipient, resourcefulness (including financial resourcefulness), dementia symptom severity, caregiving demands, carer responses to perceived stress, depressive cognitions, negative emotions, carer health outcomes, caregiving effort scales, and COVID-19 questions comprising the 158-225 item questionnaire (bereaved caretakers are not asked all study measures since they are no longer actively caring for their family member). Demographic information will also be collected (e.g. occupation, annual income, education, and questions about the care recipient such as age, number of years diagnosed with dementia, specific diagnoses, and questions related to the participant's caring of their family member with dementia). The third, and final, data collection session involves the additional measure of an Intervention Evaluation Questionnaire that will ask participants for feedback regarding the intervention they received.

The table below shows which study instruments are administered at each time point:

Data Collection Instrument	Baseline / T1	4-6 months post-intervention / T2	12-4-6 months post-T2 / T3
Demographic and Descriptive Data*	X	X	X
Health Rating of Elder Care Recipient**	X	X	X
Cultural Justification for Caregiving	X	X	X
Resourcefulness Scale	X	X	X
Financial Resourcefulness	X		
Revised Social Readjustment Rating Scale	X	X	X
Revised Memory and Behavior Problems Checklist**	X	X	X
Perceived Stress Scale	X	X	X
Depressive Cognition Scale	X	X	X
Negative Emotions Checklist	X	X	X
Caregiver Appraisal of Functional Capacity**	X	X	X
Health Risk Behavior Scale	X	X	X
PROMIS Global Health Measures	X	X	X

HRP-503SBER	TEMPLATE: SBER Protocol		
Approved:	01/2019	Prior Version:	05/2018

Caregiving Effort Scales	X	X	X
Financial Stress	X		
COVID-19 Questions	X	X	X
Intervention Evaluation Questionnaire			X
Heart Rate Variability	X	X	X

* Questions 7-13 of the Demographics will NOT be asked to caretakers.

** These scales will NOT be asked to caretakers.

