INTERVENTION: Within two weeks of the first data collection session (including study scales and HRV data collection), carers within each of the three caregiving phases (caregivers, care partners, and caretakers) will be randomly assigned using a computer program to one of three treatment groups: 1) Self-management (SM) need, 2) Self-management (SM) preference, or 3) attention control. The SM-need group will receive a self-management intervention tailored to meet their need for resourcefulness training (RT) or biofeedback (BF) as

HRP- 503SBER	TEMPLATE: SBER Protocol		
Approved:	01/2019	Prior Version:	05/2018

determined by whichever baseline cut score is lower, the Resourcefulness Scale or the SDNN parameter for age and gender. Carers randomly assigned to the SM-preference will choose to do RT or BF according to their personal preference. However, we will use minimization methods for group assignment to ensure equivalent representation across the three treatment groups, and factors likely to affect variables of interest, including carer age, gender, and race/ethnicity, in order to insure demographic similarity.

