Prior to testing the study aims, demographic profiles for caregivers, care partners, and caretakers will be created through univariate descriptive statistics, including means, standard deviations, and range of scores, and will be used to assess continuous data; frequencies and percentages will be used to describe categorical data. We will track the health conditions and the life events of all carers and dementia symptoms, level of care, and health rating of the care recipient for those who are not bereaved. However, the primary aim (**Aim 1**) is to test the effects of health self-management interventions (RT or BF) delivered based on need (i.e., cut score) or preference (i.e., personal choice) of dementia carers who have transitioned within six months to a new phase in the caregiving career (to at-home caregiver, to care partner with a facility, or to caretaker following the death of care recipient). **Aim 1** is to compare carers who are randomly assigned to the need (SM-need, preference (SM-preference) group, or an attention control condition over 3 time points (baseline, 6 months, and 12 months) on carer responses (i.e., perceived stress, depressive cognitions, and negative emotions) (**Aim 1a**), and health outcomes (health risk, and physical and mental health) (**Aim 1b**). **Aim 2** will focus on comparing caregivers, care partners, and caretakers. For **Aims 2a and 2b**, we will determine whether differences exist among caregivers, caregivers, care partners, and caretakers in carer responses (**2a**) and health outcomes (**2b**) over time. For all analyses, we will control for the effects of three covariates: months in caregiver, care partner, or caretaker role, dementia symptom severity, and caregiving demands.

For both study aims, we will use a 3 group by 3-time point Repeated Measures Analysis of Variance (RMANOVA), as well as 3 group by 3-time point Repeated Measures Analyses of

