Covariance (RMANCOVA) to control for the three covariates on carer responses (i.e., perceived stress, depressive cognitions, and negative emotions) (**Aim 1a and Aim 2a**) and health outcomes (health risk, and physical and mental health) (**Aim 1b and 2b**). We will use both analyses in a two-step process: first, we will use RMANOVA to determine if mean differences exist among the 3 groups over 3 time points. If we find mean differences, for the second step we will run RMANCOVA to identify how the covariates impact the initial findings. This controls for any confounding effects of the covariates on the repeated measures models and will also allow us to determine how much of an impact the covariates have on carer responses and health outcomes.

The RMANOVA and RMANCOVA will allow us to not only assess mean differences across time, group differences, and the interaction of time X group in order to test the trend of the means over time across the SM- need, SM-preference, and attention control condition in **Aim 1** and caregiver vs. care partner vs. caretaker in **Aim 2**. The RMANOVA and RMANCOVA not only can be used to determine if there are mean differences across the three time periods, but can also utilize orthogonal polynomial contrasts to determine whether linear and quadratic trends of the means across time are significant.

Confidentiality of Data

1. To maintain the confidentiality of the data:

I will use a unique study identifier to code individuals' identifiable data and will store the master list separate from the study data..

Other (please explain)

Provide a plan to destroy identifiers including how and when.

Identifiers in the Screening log (Box.com) and Contact Form (REDCap and CWRU BOX) will be destroyed after data collection is complete, and before the study is closed, by deleting the files.

How are you storing your electronic data?

UH Redcap

CWRU Redcap

Secure Research Environment (SRE)

CWRU Box

OnCore

UH Secure Network Drive

CWRU Secure Network Drive

Other - List storage method and provide justification:

2. Storage location of the paper research data and documents, if applicable:

Paper research data and documents will be stored in a double-locked secure environment in the following location:

France Payne Bolton School of Nursing – Health Research Campus study office

3. Will data be shared?
 Yes
1. List the exact data elements that will be shared:
2. Describe how data will be sent:
 No
 N/A

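### Aim 1 predicts that the self-management arms do better than attention control, but the plan gives only non-directional omnibus tests, no contrast with control, and no ranking of group against time by group.

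*Combined protocol and SAP*

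**What the plan says.** The Objectives section states a directional hypothesis: carers given either intervention by need or preference "will have better health outcomes than carers in the attention control condition, regardless of caregiving phase".

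The Data Analysis Plan compares SM-need, SM-preference and attention control at baseline, 6 and 12 months with a 3 x 3 RMANOVA, followed by RMANCOVA if differences are found. Step one is worded: "first, we will use RMANOVA to determine if mean differences exist among the 3 groups over 3 time points". The next paragraph says the models assess differences across time, "group differences, and the interaction of time X group in order to test the trend of the means over time", naming the three arms for Aim 1. It adds that they "can also utilize orthogonal polynomial contrasts to determine whether linear and quadratic trends of the means across time are significant". These trends are the only contrasts named. No pairwise, pooled or post-hoc comparison with attention control appears anywhere.

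On covariates, the plan says "we will control for the effects of three covariates: months in caregiver, care partner, or caretaker role, dementia symptom severity, and caregiving demands". Phase is not in the Aim 1 model, although the Intervention section says "carers within each of the three caregiving phases (caregivers, care partners, and caretakers) will be randomly assigned using a computer program", with minimisation on carer age, gender and race/ethnicity. The Data Analysis Plan tracks "dementia symptoms, level of care, and health rating of the care recipient for those who are not bereaved", and a footnote to the instrument table says of the marked care-recipient scales: "These scales will NOT be asked to caretakers".

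**The concern.** The hypothesis concerns direction and a particular comparator. A three-arm omnibus test speaks to neither. A significant time-by-group result says that the arms changed differently. It does not say which arm differs from control, or whether it did better or worse. With no contrast written down, the comparison (each arm or pooled), the visit and any correction would be chosen after the data are known.

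A second, smaller matter is that group differences are listed beside time by group without saying which one decides. The two are not interchangeable. The group main effect averages over all three time points, including T1, which is measured before randomisation. A difference present only at T2 and T3 therefore enters at two thirds of its size.

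**Working it through.** **Inputs.** From the documents: N = 350 (Number of Research Participants), three arms, three time points, and three health outcomes under Aim 1b (health risk, physical health, mental health). The plan gives no alpha, effect size, SD, within-person correlation r or dropout, so it has no power figure to reproduce. Assumed for illustration: equal arms (n = 350/3 = 116.7), SD 1, compound symmetry, alpha 0.05, no dropout, both SM arms 0.30 SD better than control at T2 and T3, and r from 0.3 to 0.7.

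**Formulas, worked at r = 0.6.** The post-baseline arm deviations are 0.1, 0.1 and -0.2, with sum of squares 0.06.

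- *Group main effect.* Averaging over T1 to T3 turns 0.30 into 0.20, so the sum of squares is 0.06 x 4/9 = 0.0267. Noncentrality = 116.7 x 0.0267 / [(1+2r)/3] = 3.11/0.733 = 4.24; df 2, 347; power 0.434.
- *Time by group.* The time deviations are -2/3, 1/3, 1/3 (sum of squares 2/3), so the interaction sum of squares is 0.06 x 2/3 = 0.04. Noncentrality = 116.7 x 0.04/(1-r) = 11.67; df 4, 694; power 0.787.
- *T1-adjusted by-visit test.* The covariance of (T2, T3) given T1 has diagonal 1-r² = 0.64 and off-diagonal r-r² = 0.24. Noncentrality = 116.7 x 0.06 x 2/(0.64+0.24) = 15.9; df 4, 692; power 0.908.
- *Each SM arm v control, T2-T3 average, two-sided 0.025.* Variance (1+r)/2 - r² = 0.44; SE = sqrt(2 x 0.44/116.7) = 0.0869; 0.30/0.0869 = 3.45; power 0.885.
- *Each SM arm v control, one visit, two-sided 0.025.* Variance 0.64; SE 0.105; power 0.730.
- *Pooled SM v control, T2-T3 average, two-sided 0.05.* SE = sqrt(0.44 x (1/233.3 + 1/116.7)) = 0.0752; power 0.978.

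| Power at r = | 0.3 | 0.4 | 0.5 | 0.6 | 0.7 |
|---|---|---|---|---|---|
| Group main effect | 0.567 | 0.515 | 0.472 | 0.434 | 0.402 |
| Time by group | 0.514 | 0.587 | 0.678 | 0.787 | 0.901 |
| T1-adjusted by-visit, 4 df | 0.817 | 0.833 | 0.864 | 0.908 | 0.958 |
| Each arm, average, 0.025 | 0.791 | 0.807 | 0.838 | 0.885 | 0.941 |
| Each arm, one visit, 0.025 | 0.560 | 0.599 | 0.653 | 0.730 | 0.830 |
| Pooled, average, 0.05 | 0.941 | 0.948 | 0.962 | 0.978 | 0.993 |

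**Direction.** The sum of squares 0.06 is the same when both SM arms are 0.30 SD better, only one is better, only one is worse, or both are worse. The time-by-group power is therefore identical in all four cases. If one SM arm is 0.30 SD better and the other 0.30 SD worse, so that the average SM effect is zero, time by group is significant with probability 0.995 at r = 0.5.

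**If either effect may count.** Under the null the two F tests are close to independent: 1 - 0.95² = 0.0975. Simulation with 117 per arm gave 0.098 (r = 0.6, 20,000 runs) and 0.094 (r = 0.5, 10,000 runs). Leaving phase out makes the group test conservative, so the true figure may be lower.

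**The case against.** The strongest reply is that the ambiguity over the deciding effect is slight. The Data Analysis Plan ties time by group to the three arms of Aim 1, and the step-one wording reads naturally as the same test. That stands. A reader might infer that Aim 1 lacks a valid test, or that the plan runs at a 10% error rate. The documents support neither: the interaction is planned, and nothing says that a bare group effect would count as success.

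Three other strong readings also fail:

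- *The group effect is always weaker.* At r = 0.3 the order reverses (0.567 v 0.514), and the documents give no r.
- *The multiplicity problem covers six outcomes.* The directional prediction concerns health outcomes, which the plan defines as three. Carer responses (Aim 1a) are examined without a stated direction. For three independent outcomes tested without correction, the chance of any false time-by-group result is 1 - 0.95³ = 14%.
- *Baseline information goes unused.* Time by group already uses T1 as a repeated measure. What is given up is the further gain from covariate adjustment.

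It can also be said that the hypothesis may mean the two SM arms pooled. That is a fair reading, and the documents do not settle it. Finally, the intervention lasts four weeks and later use is optional, so a fading effect is plausible. A contrast on the T2-T3 average would then lose power. None of this supplies the missing comparison with control.

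**Conclusion.** The point holds in limited form and should be acted on. The planned time-by-group test is valid but cannot by itself support a claim that self-management is better than attention control. This rests on the form of the test and not on any assumed effect size. The unranked group effect is a lesser gap: up to about 10% error per outcome, and only if either effect were allowed to count.

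The power figures are illustrative and depend on the assumptions listed. For a sustained 0.30 SD effect, the T1-adjusted by-visit test exceeds time by group at every r tried (0.82 to 0.96 v 0.51 to 0.90). It also does so at r = 0.6 for a fading effect of 0.30 then 0.10 SD (0.76 v 0.66) and for an effect at T2 only (0.83 v 0.79). At 0.50 SD sustained, time by group already reaches 0.99 or more for r of 0.5 and above, so the gain there is negligible.

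A reader might also infer that the covariate adjustment will drop all caretakers. The plan does not say which scales supply severity and demands, so this is a conditional risk only.

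**What to change.** For Aim 1, model T2 and T3 by visit, with the T1 value of the same outcome as covariate (or with arm means constrained equal at T1). Include phase, carer age, gender and race/ethnicity.

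Before outcomes are seen, declare the comparison with control that decides Aim 1, at one named visit or on the T2-T3 average. It should be one of:

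- SM-need v control and SM-preference v control, with Holm correction; or
- pooled SM v control, as a single contrast.

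Time by group and the group main effect then become supportive. State how the three health outcomes are handled (one named primary, or a correction across them), and treat carer responses separately.

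Months in role can stay in the main model. If severity and demands come from the scales not asked of caretakers, keep those two out of the main model so that caretakers are not dropped. Use their T1 values in a supporting analysis of caregivers and care partners.

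**Cost.** The change is to wording only, since the variables are already collected. Each choice has a price (r = 0.6):

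- The each-arm T2-T3 average falls to 0.52 for 0.30 then 0.10 SD, and to 0.30 for an effect at T2 only, against 0.66 and 0.79 for time by group.
- An each-arm T2 contrast keeps 0.73 in both cases but misses an effect seen only at T3.
- The pooled average falls to 0.51 if only one SM arm works, because the pooled effect is then 0.15 SD.
- Correction across outcomes, if chosen, costs further power.

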The **second aim** is to determine whether differences exist among caregivers, care partners, and caretakers in carer responses (**2a**) and health outcomes (**2b**) over time. All carers will complete measures of caregiving responses and health outcomes at baseline (T1), 6 months (T2), and 12 months (T3). The four-week interventions will occur between T1 and T2 data points. Carers may use the intervention as often as they wish (i.e., self-tailoring); dosing and fidelity will be measured. Repeated measures bivariate and multivariate analyses will address the study aims while controlling for dementia symptom severity and caregiving demands.

Background

Directions: Describe the relevant prior experience and gaps in current knowledge describing how it will add to existing knowledge. Include any relevant preliminary data.

Dementia is the most under recognized health crisis of the 21st century, with over 46 million people worldwide living with dementia, a number that is expected to reach 131.5 million by 2050.⁴ In the United States, family members provide care for over 5.4 million elders with some form of dementia. Regardless of cause, dementia has a slow, progressive, fairly predictable downward course, with losses in mental and physical functioning that generate negative **carer responses** (i.e., perceived stress, depressive cognitions, negative emotions) and may seriously compromise the family carer's health risks and physical and mental health (i.e., **health outcomes**). Research shows that within six months of a transition to a new caregiving phase (i.e., from caregiver, to care partner, to caretaker), the health of family carers shows evidence of substantial decline. Although researchers have identified factors occurring throughout the caregiving career that may adversely affect the carer's health, interventions to promote health self-management by reducing negative caregiving responses have not been tested in carers who have recently transitioned into the role of caregiver, care partner, or caretaker. Consistent with

the Precision Medicine Initiative, which presents an innovative model that accounts for individual differences and empowers health care recipients (i.e., family carers) to participate actively in health care decisions, sustainable self-management interventions should be designed and tailored to match the carer's needs and preferences and then tested with randomized, controlled trials.

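### The plan promises covariate control for all analyses but fits the adjusted model only after an unadjusted RMANOVA finds unspecified mean differences, so a null first step could leave the non-randomised Aim 2 phase comparison unadjusted

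*Combined protocol and SAP*

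**What the plan says.** Three places promise adjustment without any condition.

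- Data Analysis Plan, end of the first paragraph: "For all analyses, we will control for the effects of three covariates". These are months in the current role, dementia symptom severity and caregiving demands.
- Objectives, second aim: "Repeated measures bivariate and multivariate analyses will address the study aims while controlling for dementia symptom severity and caregiving demands".
- Background, closing paragraph: the list of what the study will do includes controlling for the same three covariates.

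The Data Analysis Plan then sets a two-step rule for both aims. Step 1 is unadjusted: "first, we will use RMANOVA to determine if mean differences exist among the 3 groups over 3 time points". Step 2 is conditional: "If we find mean differences, for the second step we will run RMANCOVA to identify how the covariates impact the initial findings". The plan says of this process: "This controls for any confounding effects of the covariates on the repeated measures models". The next paragraph says the models will "assess mean differences across time, group differences, and the interaction of time X group". It does not say which of these effects triggers step 2, or at what significance level.

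Two other facts bear on the point. Under Study Design/Procedures (Intervention), carers are randomised to treatment within each phase, so phase itself is not randomised. In the instrument table of the same section, the memory and behaviour checklist and the functional-capacity appraisal carry a footnote: "These scales will NOT be asked to caretakers". A second footnote reads: "Questions 7-13 of the Demographics will NOT be asked to caretakers".

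**The concern.** After a null step 1 the analyst has two instructions that cannot both be followed: adjust always, or stop.

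The conflict matters most for Aim 2. Covariate imbalance between non-randomised groups can hide a difference as easily as create one. A gate on the unadjusted test sends only apparent differences to adjustment and never examines apparent nulls. If the group test is the trigger and it is null, no adjusted phase comparison is fitted, and the plan's statement about controlling confounding is then untrue. A finding of no difference between phases could still be described as covariate-controlled on the strength of the unconditional promise.

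**Working it through.** **Figures in the plan.** The Data Analysis Plan gives no alpha, effect size, SD or covariate relationship, so there is nothing to reproduce. What follows is an illustration.

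**Input from the documents.** The target is 350 carers. An equal split is assumed: 350/3 = 116.7, taken as 117 per phase.

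**Assumed inputs.** Two-sided alpha 0.05; residual SD 1; adjusted caregiver versus care partner difference 0.4 SD; one covariate with SD 1 and slope 0.4; covariate mean shifted 0.5 SD between these two phases in the opposing direction; three time points averaged; within-person residual correlation 0.5. Caregivers and care partners are the contrast because severity and demands are measured in both.

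**Step 1: what the unadjusted model sees.** The apparent difference is 0.4 − 0.4 × 0.5 = 0.2. The residual variance of a three-time-point mean is 0.5 + 0.5/3 = 0.667. Adding the covariate gives 0.667 + 0.4² = 0.827.

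**Step 2: always-adjusted power.** SE = √(0.667 × 2/117 × (1 + 0.5²/4)) = √(0.667 × 0.01709 × 1.0625) = 0.110. Then 0.4/0.110 = 3.64, which gives power of about 95%.

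**Step 3: the plan's gate, a three-phase group test.** The noncentrality is λ = 117 × Σ(mean − grand mean)²/0.827, on 2 and 348 degrees of freedom. Unadjusted means are 0 for caregivers and 0.2 for care partners; the caretaker mean is varied. Gated power needs the gate to open and the adjusted contrast to be significant (simulation, 5,000 datasets per row).

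| Caretaker mean above caregivers (SD) | λ | Gate opens | Gated power | Always adjusted |
|---|---|---|---|---|
| 0 | 3.77 | 39% | about 38% | about 95% |
| 0.2 | 3.77 | 39% | about 39% | about 95% |
| 0.3 | 6.60 | 62% | about 60% | about 95% |
| 0.4 | 11.32 | 86% | about 83% | about 95% |
| 0.5 | 17.93 | 97% | about 92% | about 95% |

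**Step 4: a different trigger.** Suppose any of group, time or interaction opens the gate and caretakers equal caregivers. Gated power is then about 62%, 91% and 95% for a common T1-to-T3 trend of 0.1, 0.2 and 0.3 SD. The choice of trigger, which the plan leaves open, therefore changes the result substantially.

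**Step 5: where little or nothing is lost.** With a same-direction shift of 0.5 SD the apparent difference is 0.4 + 0.2 = 0.6, the gate almost always opens, and there is no loss. For a group-by-time contrast (T1-to-T3 change, difference 0.4 SD, opposing 0.5 SD shift, two-phase test), gated power is 83% against 84% always adjusted.

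**The case against.** **Both models may always be intended.** The plan introduces RMANOVA together with RMANCOVA, which could mean that both are run regardless. The following sentences, however, explain how they are combined, and the second carries an explicit condition. If the sponsor did mean both, removing that clause costs nothing.

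**The consequence is narrow.** It concerns mean levels in the second aim, after a null step 1, with covariate shifts that oppose the true difference. If group differences are the trigger, a phase difference declared at step 1 does go on to adjustment, so the exposure is a missed difference and not an unadjusted positive claim. The Background also expects carers' health to fall after a transition; if a time effect opens the gate, such a trend shrinks the loss. All of this stands and limits the weight of the point.

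**Adjustment may not be the right target.** The Background treats level of care as reflected in the phases, so demands may be part of what phase means, and an unadjusted contrast is then a legitimate quantity. This supports reporting both models; it does not support choosing between them by a significance test.

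**Stronger readings.** A reader might infer that the gate undermines Aim 1. It does not: the arms are randomised and adjustment there mainly buys precision. A reader might infer that a masked phase difference would be missed as a rule. The documents support only that it could be: they give neither size nor direction for any covariate shift. A two-phase gate at a single time point gives a starker contrast (29% against 84% under the same difference, slope and shift), but the plan's step 1 is a three-phase, three-time-point test, so that figure does not describe it.

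**Conclusion.** The contradiction between unconditional and conditional adjustment is plain from the text, and the trigger is not tied to a named effect. It should be corrected, though it does not threaten the primary aim.

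The practical risk is confined to the Aim 2 comparison of phase mean levels. Under the assumed values, power for the caregiver versus care partner difference falls from about 95% to about 38% when caretakers lie close to the other phases. It falls only to about 92% when the caretaker mean is 0.5 SD above caregivers. The loss shrinks further if a time effect can open the gate. These figures rest on an equal split, a single covariate, a slope of 0.4 and an opposing shift of 0.5 SD, none of which the documents supply beyond the total of 350. They show that the loss can be large, not that it will be.

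**What to change.** 1. In the Data Analysis Plan, delete the conditional clause that opens "If we find mean differences, for the second step we will run RMANCOVA to identify how the covariates impact the initial findings". Fit and report the adjusted model beside the unadjusted one for every outcome, whatever step 1 shows, and name the main model for each aim in advance.
2. Amend "For all analyses, we will control for the effects of three covariates" and the matching statements in Objectives and Background. The symptom and functional-capacity scales, which by inference supply the severity and demands covariates, are not given to caretakers, so the promise cannot be met as written.
3. For Aim 2, adjust three-phase models only for covariates collected in all phases, such as months in role. Confirm first that this is collected from caretakers, because the Demographics questions withheld from them are not listed. Add a caregiver versus care partner analysis adjusted for severity and demands.
4. For Aim 1, use T1 covariates available in all carers, with a severity- and demands-adjusted model in non-bereaved carers as a supporting analysis.

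**Cost.** One rewritten paragraph, amended sentences in three sections, one extra model per outcome, the added two-phase analysis and the supporting Aim 1 model. Pooled Aim 1 models and every comparison involving caretakers stay unadjusted for severity and demands. In the planned three-phase Aim 2 test, removing the gate restores at most months in role; the gain illustrated above belongs to the two-phase analysis. Because demands may be part of what phase means, both adjusted and unadjusted phase contrasts should be shown.
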